18.2 Calculation Using Dates

Calculations using dates (e.g., subject's age or relative day after the first dose of study drug) will adhere to the following conventions:

- Study days after the start day of study drug will be calculated as the difference between the date of interest and the first date of dosing of study drug plus 1 day. The generalized calculation algorithm for relative day is the following:
 - If TARGET DATE \geq DSTART then STUDY DAY = (TARGET DATE – DSTART) + 1;
 - Else use STUDY DAY = TARGET DATE – DSTART.

Note that Study Day 1 is the first day of treatment of study drug. Negative study days are reflective of observations obtained during the baseline/screening period. Note: Partial dates for the first study drug are not imputed in general. All effort should be made to avoid incomplete study drug start dates.

- Age (expressed in years) is calculated as the number of months between birth date and informed consent date divided by 12 (if both dates are not missing), the integer part will be kept. If the month of birth date is the same as informed consent date and the day of birth date is greater than informed consent date, then the age calculated by above will minus 1. If any date is missing, AGE will be set to the age collected from CRF.

- Partial birth date: impute missing day as 15th of the month; impute missing month as July; set missing age for missing year

- Intervals that are presented in weeks will be transformed from days to weeks by using (without truncation) the following conversion formula: $WEEKS = DAYS / 7$
- Intervals that are presented in months will be transformed from days to months by using (without truncation) the following conversion formula:

$$MONTHS = DAYS / 30.4167$$

18.3 Date Imputation Guideline

Impute Missing Adverse Events/ Prior or Concomitant Medications, Procedures/Surgeries as follows:

Incomplete Start Date:

Missing day and month

- If the year is the **same** as the year of the first dosing date, then the day and month of the first doing date will be assigned to the missing fields.
- If the year is **prior to** the year of first dosing date, then December 31 will be assigned to the missing fields.
- If the year is **after** the year of first dosing, then January 1 will be assigned to the missing fields.

Missing day only

- If the month and year are the **same** as the year and month of first dosing date, then the first doing date will be assigned to the missing day.

- If either the year of the partial date is **before** the year of the first dosing date or the years of the partial date and the first dosing date are the same but the month of partial date is **before** the month of the first dosing date, then the last day of the month will be assigned to the missing day.
- If either the year of the partial date is **after** the year of the first dosing date or the years of the partial date and the first dose date are the same but the month of partial date is **after** the month of the first dosing date, then the first day of the month will be assigned to the missing day.
- If the stop date is not missing, and the imputed start date is after the stop date, the start date will be imputed by the stop date.

Missing day, month, and year

- No imputation is needed, the corresponding AE will be included as TEAE.

Incomplete Stop Date: If the imputed stop date is before the start date, then the imputed stop date will be equal to the start date.

Missing day and month

- If the year of the incomplete stop date is the **same** as the year of the last dosing date, then the day and month of the last dosing date will be assigned to the missing fields.
- If the year of the incomplete stop date is **prior to** the year of the last dosing date or prior to the year of the first dosing date, then December 31 will be assigned to the missing fields.
- If the year of the incomplete stop date is **prior to** the year of the last dosing date but is the same as the year of the first dosing date, then the first dosing date will be assigned to the missing date.
- If the year of the incomplete stop date is **after** the year of the last dosing date, then January 1 will be assigned to the missing fields.

Missing day only

- If the month and year of the incomplete stop date are the **same** as the month and year of the last dosing date, then the day of the last dosing date will be assigned to the missing day.
- If either the year of the partial date is **not equal to** the year of the last dosing date or the years of the partial date and the last dosing date are the same but the month of partial date is **not equal to** the month of the last dosing date, then the last day of the month will be assigned to the missing day.

Celgene Signing Page

This is a representation of an electronic record that was signed electronically in Livelink.
This page is the manifestation of the electronic signature(s) used in compliance with
the organizations electronic signature policies and procedures.

UserName: [REDACTED]
Title: [REDACTED]
Date: Thursday, 11 March 2021, 01:18 PM Eastern Daylight Time
Meaning: Approved, no changes necessary.
=====

UserName: [REDACTED]
Title [REDACTED]
Date: Friday, 12 March 2021, 12:42 AM Eastern Daylight Time
Meaning: Approved, no changes necessary.
=====

UserName: [REDACTED]
Title: [REDACTED]
Date: Friday, 12 March 2021, 10:22 AM Eastern Daylight Time
Meaning: Approved, no changes necessary.
=====

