All AEs regardless of causality will be recorded by the Investigator from the time the subject signs informed consent until 9 weeks after the last dose of IP as well as those SAEs made known to the Investigator at any time thereafter that are suspected of being related to IP. In addition, AEs that are suspected to be related to the IP as well as new malignancies or pre-malignancies regardless of causality (see Section 10.5.2) will be recorded by the Investigator until 156 weeks after the last dose of IP. Information will be collected as described in the Table of Events, Table 3 and Section 6.6. AEs and SAEs will be recorded on the AE page of the eCRF and in the subject's source documents. All SAEs must be reported to Celgene Drug Safety within 24 hours of the Investigator's knowledge of the event by facsimile, or other appropriate method, using the SAE Report Form, or approved equivalent form.

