11.1 Adverse Events

Adverse events will be analyzed in terms of treatment-emergent adverse events (TEAEs) which are defined as any AEs that begin or worsen on or after the start of study drug through 63 days after the last dose of IP (i.e., AE start date on or after the first dose date and within last dose date + 63). In addition, an AE that occurs beyond this timeframe and that is assessed by the investigator as possibly related (suspected) to study drug will be considered to be treatment-emergent.

All AEs will be coded using the MedDRA (Version 23.0). The incidence of TEAEs will be summarized by MedDRA SOC and PT. The AE tables will be sorted by SOC and PT (within SOC) in descending frequency within the luspatercept group. If a subject experiences multiple AEs under the same PT (or SOC), then the subject will be counted only once for that PT (or SOC).

The intensity of AEs will be graded 1 to 5 according to the National Cancer Institute Common Terminology Criteria for Adverse Events (CTCAE) Version 4.0. If a subject experiences the same AE more than once with different toxicity grades, then the event with the highest grade will be tabulated in “by grade” tables. In addition, AEs with a missing intensity will be presented in the summary table as an intensity category of “Missing” only if the same event category has no other valid grades.

Tables summarizing the incidence of TEAEs will be generated for each of the following by treatment group (if not otherwise specified, the summary is by SOC and PT):

- TEAEs;
- TEAEs by SOC only;
- Treatment-related TEAEs;
- Serious TEAE;
- Treatment-related serious TEAEs;
- TEAEs by CTCAE maximum severity;
- Treatment-related TEAEs by CTCAE maximum severity;
- TEAE with CTCAE Grade ≥ 3 ;
- Treatment-related TEAE with CTCAE Grade ≥ 3 ;
- TEAEs leading to study drug discontinuation;
- Treatment-related TEAEs leading to study drug discontinuation;
- TEAEs leading to study drug dose reduction;
- Treatment-related TEAEs leading to study drug dose reduction;
- TEAEs leading to study drug dose delay;
- Treatment-related TEAEs leading to study drug dose delay;
- TEAEs leading to death;
- Treatment-related TEAEs leading to death;
- Most frequent TEAEs by PT ($\geq 5\%$ in PT frequency of all subjects or subjects from any treatment group); Most frequent TEAEs by SOC ($\geq 5\%$ in SOC frequency of all subjects); Most frequent TEAEs by SOC and high level term (HLT) ($\geq 5\%$ in HLT frequency of all subjects)

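### SAP 18.3 counts an adverse event with no start date as treatment-emergent even when its stop date precedes the first dose; as the list is laid out, a year-only start in the first-dose year is treated the same way

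*SAP*

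**What the plan says.** SAP 11.1 defines treatment-emergence by onset or worsening on study drug, and puts it in operational terms as "AE start date on or after the first dose date and within last dose date + 63". Events beyond that window count only if suspected to be related.

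SAP 18.3 gives three lists for incomplete start dates:

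- **Day and month missing.** If the year is that of the first dose, "then the day and month of the first doing date will be assigned to the missing fields" (the first dosing date is meant). An earlier year becomes 31 December of that year, a later year 1 January.
- **Day missing.** The rules are similar, by month. The last bullet adds that, where the stop date is known and "the imputed start date is after the stop date, the start date will be imputed by the stop date".
- **Everything missing.** "No imputation is needed, the corresponding AE will be included as TEAE".

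For incomplete stop dates, the consistency rule stands beside the heading, above its lists: "If the imputed stop date is before the start date, then the imputed stop date will be equal to the start date".

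Events from before dosing are in the same log. Protocol 10.1 says "All AEs regardless of causality will be recorded by the Investigator from the time the subject signs informed consent", and Protocol 3.1.1 sets a Screening/Run-in Period of at least 12 weeks. SAP 11 bases the safety summaries on all collected records unless otherwise specified.

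**The concern.** Counting an event of unknown onset as treatment-emergent is a sound default when the timing cannot be settled. Here the record can settle it: an event that stopped before the first dose cannot have begun or worsened on study drug. SAP 18.3 ignores that information when the start is wholly missing and, as the list is laid out, when only the year is known and it is the first-dose year. I found no other rule in either document that removes such an event.

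TEAE status feeds the overall, serious, Grade 3 or higher and special-interest tables (SAP 11.1 and 11.2). SAP 11.3 also sums bone-pain duration in days within a subject, and a start later than its stop would put a negative term into that sum.

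**Working it through.** The plan states no figure here, so the check is to run the rules on test records.

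**Inputs.** The start-date rules are from SAP 18.3 and the TEAE definition from SAP 11.1. The dates are assumed for illustration: first dose 01SEP2016, recorded stop 20JUL2016. Reading (a) confines the stop-date check to the list in which it stands. Reading (b) applies it to every imputed start date.

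| Start date as recorded | Reading (a): start used, class | Reading (b): start used, class |
|---|---|---|
| wholly missing | none, TEAE | none, TEAE |
| 2016 | 01SEP2016, TEAE | 20JUL2016, not a TEAE |
| JUL2016 | 20JUL2016, not a TEAE | 20JUL2016, not a TEAE |
| 10JUL2016 (complete) | 10JUL2016, not a TEAE | 10JUL2016, not a TEAE |

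All four rows could describe one event. The wholly missing case is misclassified under both readings, since there is no imputed start for the check to act on. The year-only case is misclassified under reading (a) alone.

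**Negative duration, reading (a), year-only start.** The imputed start is 43 days after the stop (11 days left in July + 31 in August + 1). If duration is stop − start + 1, a formula that SAP 11.3 does not state, the result is −43 + 1 = −42 days. The rule beside the stop-date heading does not repair this, because it acts on imputed stop dates and this one is complete.

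**Reach of the year-only rule.** Assume an 84-day run-in and first doses spread evenly over a 366-day year. The j-th day before the dose falls in the dose's calendar year with probability (366 − j)/366. Averaged over j = 1 to 84, this is 1 − 42.5/366 = 0.884. About 88% of run-in days would share the first-dose year. This describes where the rule can apply, not how often a date is incomplete.

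**Order of operations.** Take a start of 2016, a stop of JUL2016 with the day missing, and the same first dose. The stop is imputed as 31JUL2016 (for a last dose in any other month). The start is imputed as 01SEP2016. The rule beside the stop-date heading then moves the stop to 01SEP2016, and the evidence that the event ended before dosing is lost. Any correction must act before that step.

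**The case against.** **Placement of the check.** The stop-date bullet is worded generally, and nothing in it is peculiar to a missing day. It comes just before the case in which nothing is imputed, so it may have been meant to close all the imputed cases, with its list level lost in layout or extraction. This stands as a possible reading. It would remove the year-only case and the negative durations, but not the wholly missing case. Against it, the corresponding stop-date rule does stand at heading level, so a programmer could fairly take the start-date bullet as confined to its list.

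**Rarity.** SAP 18.1 expects log dates to be complete unless the event is ongoing, and Protocol 10.2.4 requires start and stop dates for every event. SAP 11.1 counts a subject once per term, so a misclassified event alters a row only if that subject has no other TEAE with the same term. SAP listings flag TEAEs and show dates as recorded, so the anomaly can be seen. All of this stands, and it keeps the point small.

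**Stronger readings that the documents do not support.**

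- *A count.* A reader might take 300 subjects with one or two run-in events each, and 0.5% to 2% of those with such dates, giving 300 × 0.005 = 1.5 up to 600 × 0.02 = 12 events. Both rates are assumptions, and neither document supplies one.
- *The run-in as a large share of follow-up.* For 48 weeks of treatment it is 12/(12 + 48 + 9) = 17.4% of the collection period. This SAP serves the final CSR, and for a subject treated to Week 228 the share is 12/(12 + 228 + 9) = 4.8%.
- *Greatest harm for serious events.* These are the least likely to lack dates, because Protocol 10.2.1 requires start and stop dates for each SAE and Protocol 10.5 requires a report within 24 hours.
- *A diluted treatment contrast.* The rule is the same in both arms and the run-in precedes randomization, so the contrast barely moves.

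**Conclusion.** The point holds as a minor error in a stated rule. SAP 18.3 contradicts SAP 11.1 for an event with a wholly missing start and a recorded stop before the first dose, whichever way the list is read. For a year-only start in the first-dose year, the contradiction and the possible negative duration hold on the text as laid out, and disappear if the stop-date check was meant for all imputed starts.

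The size cannot be computed from the documents. It is probably a few run-in events wrongly included in TEAE tables, with little effect on the comparison between arms. That judgement rests on log dates being largely complete, as SAP 18.1 expects.

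**What to change.** In SAP 18.3:

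1. Move the stop-date check to the heading for incomplete start dates, so that it covers every imputed start.
2. Add to the wholly missing rule: *unless the recorded stop date is before the first dose date*.
3. Apply both to complete stop dates. Apply them to a partial stop date only when its recorded month and year, or its year alone, lie wholly before the first dose.
4. State that this is done before an imputed stop date is moved forward to the start date.

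Events that are ongoing, have an unknown stop date, or stop on or after the first dose remain TEAEs, so the conservative default is kept wherever timing is in doubt. While editing, correct the reference in SAP 18.1, which sends the reader to Appendix 17.2 for rules that stand in 18.3.

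The cost is a sentence or two and one program condition. The small downside is that any event reclassified relative to the primary CSR needs a footnote. The SAP for that report is not among the documents, so whether it used the same rule cannot be checked here.

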11.3 Other Adverse Events That Require Safety Analysis

Other adverse events that require safety analysis include AEs that fall under the “Embolic and Thrombotic Events” SMQ category and AEs with PT “Bone pain”.

Similar to AESI, summary will be provided for AEs that fall under the “Embolic and Thrombotic Events” SMQ category by preferred term. For “Bone pain” events, number of subjects with bone pain events by worst CTCAE grade will be provided from grade 1 to grade 3. The number and percentage of subjects with bone pain occurred during the first 24 weeks and after 24 weeks will be provided. Summary statistics will also be provided for time to first bone pain, total duration of bone pain (in days), total duration of bone pain that occurred during the first 24 weeks (in days), and total duration of bone pain that occurred after 24 weeks (in days). Total duration of bone pain is defined as sum of all bone pain duration within a subject, excluding overlapped period.

The “Embolic and Thrombotic Events” SMQ category analysis will include subgroup analysis by splenectomy status, platelet above ULN, concomitant medications, and comorbidities as needed.

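### SAP 18.3 has two overlapping stop-date rules with no stated precedence; one cuts an on-treatment event to a single day when the last dose falls in a later calendar year than the first

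*SAP*

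**What the plan says.** SAP 18.3, under Incomplete Stop Date with day and month both missing, has four bullets:

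1. Stop year equal to the last-dosing year: the stop takes the last dosing date ("the year of the last dosing date, then the day and month of the last dosing date will be assigned to the missing fields").
2. Stop year before the last-dosing year "or prior to the year of the first dosing date, then December 31 will be assigned to the missing fields".
3. Stop year before the last-dosing year "but is the same as the year of the first dosing date, then the first dosing date will be assigned to the missing date".
4. Stop year after the last-dosing year: 1 January.

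A floor sits above all four: "If the imputed stop date is before the start date, then the imputed stop date will be equal to the start date".

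Where only the day is missing, the same section uses the last dosing day if the month and year match the last dose, and the end of the month otherwise.

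SAP 18.1 says that incomplete log dates are imputed for purposes such as duration. It points to Appendix 17.2, but Section 17 is the reference list, so I take 18.3 to be meant. SAP 11.3 is the analysis that uses adverse event duration: "Total duration of bone pain is defined as sum of all bone pain duration within a subject". It reports this overall, for the first 24 weeks and after 24 weeks. SAP 11.1 sets the main treatment-emergent window by start date ("AE start date on or after the first dose date and within last dose date + 63").

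**The concern.** The third bullet's condition is a subset of the second's, and nothing says which one wins. Two programmers following the SAP could therefore derive different stop dates from the same record.

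Precedence is only part of the problem. The third bullet uses the first dosing date as a stop. For an event that began after first dose, that date is impossible. The floor repairs the impossibility by setting the stop equal to the start, so the event is counted as lasting one day whatever its real length. At stake are the bone-pain duration summaries, including the first-24-week figure, since much of that period falls in the first-dose year for many subjects.

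**Working it through.** The plan gives no figure on this point to reproduce. The check applies the rules as written, with duration = stop − start + 1.

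**Overlap.** Let Y be the stop year, F the first-dosing year and L the last-dosing year.

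- Second bullet: Y < L or Y < F gives 31 December of Y.
- Third bullet: Y < L and Y = F gives the first dosing date.

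If Y = F and F < L, both apply. The dates differ unless the first dose was itself on 31 December. If F = L, a stop year equal to F meets only the first bullet. For example, with first dose 10 Jan 2017 and last dose 1 Nov 2017, the stop is 1 Nov 2017 and there is no conflict.

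**Worked example (illustrative dates).** First dose 15 Feb 2017, event start 10 Mar 2017, stop recorded as 2017, last dose in 2020.

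- Second bullet: 10 Mar to 31 Dec 2017 = 22 + 30 + 31 + 30 + 31 + 31 + 30 + 31 + 30 + 31 = 297 days.
- Third bullet: the stop is 15 Feb 2017, before the start. The floor moves it to 10 Mar 2017, so the duration is 1 day.
- If the stop had been recorded as June 2017, the month-end rule would give 30 June: 22 + 30 + 31 + 30 = 113 days.

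Under the third bullet, losing the month turns a 113-day event into a one-day event.

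**Event starting before first dose.** First dose 15 Mar 2017, last dose 1 Jun 2019, start 13 Feb 2017, stop recorded as 2017. The third bullet gives 13 Feb to 15 Mar = 31 days and the second gives 322. The dates conflict, but the event does not collapse.

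**Grid check.** The rules were run over first doses at weekly steps through one year, last doses at 21-day steps over nearly 1,800 days, and starts every 5 days from 60 days before first dose to the end of the first-dose year. The stop year was always the first-dose year.

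| Set | Combinations |
|---|---|
| All | 223,342 |
| Last dose in a later year (all met both bullets) | 193,307 |
| Of these, start on or after first dose (all 1 day under the third bullet) | 144,551 |
| Of these, start before first dose (none collapsed) | 48,756 |

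These counts confirm the logic. They are not estimates of how many subjects are affected.

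**How often the last dose falls in a later year.** This rests on an assumption. If first doses are spread evenly over a calendar year and a subject receives 16 doses every 21 days, the last dose is on Day 1 + 15 × 21 = Day 316, and 315/365 = 86% have it in a later year. Beyond one year of treatment it is 100%. With early discontinuation it is lower.

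**The case against.** Several points on the other side have force.

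- **The third bullet may be a deliberate exception.** Its wording can be read as a carve-out from the second bullet. On that reading there are not two rival dates. The one-day result then becomes certain, so this changes the nature of the fault without removing it.
- **31 December is not the true stop date either.** In the example the real duration lies between 1 and 297 days. The third bullet plus the floor gives the minimum and 31 December gives the maximum. Within the first 24 weeks (15 Feb to 1 Aug 2017), the 31 December rule credits bone pain on all 145 days from 10 March. This stands, and it is why the affected records need to be reported.
- **Few records may be affected.** SAP 18.1 expects log dates to be complete unless ongoing, Protocol 10.2.4 requires start and stop dates for every event, and on-treatment visits are every 3 weeks. A stop with even the month unknown should be rare. This also stands.

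A reader might also infer more than the text supports:

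- That every such event collapses. It must start on or after first dose, and the last dose must be in a later calendar year.
- That the rule always shortens duration. That holds relative to 31 December, not to the truth. An event that began and really ended before first dose, in the same year, would be lengthened.
- That nearly all subjects meet the condition. The documents give no such figure.
- That concomitant-medication tables change. Under SAP 8.5.2, a drug started before treatment that stops on Day 1 still counts as concomitant, and one started later counts by its start date.

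**Conclusion.** The rule is wrong as written, with a narrow effect. The second and third bullets conflict whenever the stop year is the first-dosing year and precedes the last-dosing year. Applying the third gives a one-day duration to any such event that starts on or after first dose.

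The gap between the two rules can approach a year for one record (297 days against 1 in the example), but it is a difference between conventions, not a measured error. Relative to 31 December, the third bullet shortens the descriptive bone-pain durations in SAP 11.3. Treatment-emergent incidence, time to first bone pain, concomitant-medication counts, and the primary and key secondary endpoints are unaffected. The total effect cannot be computed, because the number of stop dates with day and month missing is not given.

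The conclusion assumes that 18.3 is the rule set that 18.1 refers to. It is a minor point, worth correcting because the correction is so cheap.

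**What to change.** Delete the third bullet under Incomplete Stop Date, missing day and month, so that 31 December applies whenever the stop year precedes the last-dosing year. Keep the start-date floor. This agrees with the second bullet and with the month-end convention where only the day is missing. Stating that the third bullet takes precedence would remove the ambiguity but keep the one-day result.

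Because 31 December is an upper bound, count the bone-pain records with an imputed stop, or footnote them in the duration tables.

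The cost is one deleted line and a re-run of the affected derivations, plus one check of earlier output. The SAP for the primary CSR, signed 19 June 2018, is not among the documents. The protocol's amendment rationale reports 281 subjects randomized by 4 April 2017, so most first-dose-year events precede the 11 May 2018 cutoff. If that SAP used the same rule, any bone-pain durations already reported should be checked, and any difference explained in the final CSR.
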